6.7 Safety analyses

All AEs, whether considered drug-related or not, will be reported with a diagnosis, start/stop dates, action taken, whether treatment was discontinued, any corrective measures taken, outcome, and other possible causes. For all events, the relationship to treatment and the intensity of the event will be determined by the investigator.

All AEs will be analyzed in terms of descriptive statistics and qualitative analysis. Treatment emergent adverse events will be listed for each patient and summarized by system organ class (SOC) and preferred term (PT) using the Medical Dictionary for Regulatory Activities (MedDRA).

Safety laboratory data, ECGs, physical examination findings, and vital signs measurements will be listed for each patient and presented descriptively by treatment group and time point.

Safety variables may include but not limited to the following: laboratory changes (complete blood counts, electrolytes, chemistry, and coagulation), changes in vital signs (blood pressure, heart rate, respiratory rate, and temperature), and ECG and, in some instances, as produced at the investigator's discretion.

6.8 Determination of sample size

The sample size calculation is based on the following assumptions: the weekly CSBM change from baseline is 0.5 for the placebo group, and 1.5 for each active group, with common standard deviation of 1.5; 50 patients in each group will have 90% power for each SYN-010 group compared with the placebo by using the t-test with alpha=0.05.

7. Study population

7.1 Study population and statistical assumptions

A total of 150 adult IBS-C patients will be enrolled in a single site: 50 in the Placebo group and 50 in each of the SYN-010 21 mg and SYN-010 42 mg treatment groups. The sample size calculation is based on the t-test to achieve 90% power for each SYN-010 group when compared with the placebo group.

7.2 Eligibility criteria

Patients must meet all of the following inclusion and exclusion criteria to be included in the study.

7.2.1 Inclusion criteria

- 1. Male or female participants aged between 18 and 65 years inclusive.
- 2. Patient must be willing and able to participate in the study for the required duration, understand and sign the informed consent form (ICF), and be willing to comply with all protocol-related visits and procedures.
- 3. Patient has had IBS-C symptoms (as defined by Rome IV diagnostic criteria) for at least 6 months prior to diagnosis.
- Patient has an average score of ≥ 3.0 for daily abdominal pain at its worst (11-point numerical rating scale [NRS]) during and up to the 17 days immediately before randomization (i.e. Pretreatment Period).
- 5. Patient has an average of \leq 3 CSBMs per week or \leq 5 SBMs per week during the 17 days immediately before randomization (i.e. Pre-treatment Period).
- Patient has a breath methane level ≥ 10 ppm on a lactulose breath test administered at Screening.
- 7. Patient may be on a stable, continuous regimen of fiber or probiotics one month before the Screening Visit; however, they must maintain a stable dose regimen through Week 12.
- 8. Patient must agree to refrain from starting a new diet, changing stable dose of supplemental fiber, or changing exercise pattern that may affect IBS-C symptoms from the time of Screening through the end of the study. If the patient takes food products that are strong inhibitors of cytochrome P450 3A (CYP3A) (e.g. grapefruit juice, Seville orange juice, St. John's Wort), he/she must agree to refrain from taking these from the time of Screening through the end of the study.
- 9. Patient must agree to use an acceptable method of contraception from the time of signing the ICF to 30 days after the final dose of study drug if the patient is a sexually active female of child-bearing potential (defined as any female who has experienced menarche and who is NOT permanently sterile or postmenopausal. Postmenopausal is defined as 12 consecutive months with no menses without an alternative medical cause). Adequate contraceptive measures include: oral contraceptives (stable use for two or more cycles before Screening); intrauterine device; Depo-Provera[®]; Norplant[®] System implants; partner with a vasectomy; double-barrier birth control (e.g. use of a condom plus diaphragm or condom plus either contraceptive sponge, foam, or jelly); or abstinence. According to drug research standards, male patient must agree to use an acceptable method of contraception and refrain from donating sperm from the time of signing the ICF to 90 days after the final dose of study drug.
- 10. A female patient of child-bearing potential must be non-pregnant and non-lactating and have negative pregnancy tests at the Screening Visit and on Day 1 prior to dosing with study drug.
- 11. Patients must be able to understand and be willing to sign the written informed consent form. A signed informed consent form must be appropriately obtained prior to the conduct of any trial-specific procedure.
- 12. Willing and able to comply with the protocol, including follow-up visits and examinations.

7.2.2 Exclusion criteria

Patients who meet any of the following criteria will be excluded from this study:

- Patient has loose (mushy) or watery stools for > 25% of their bowel movements (BMs) during the 12 weeks before Screening or during the Screening and Pre-treatment Periods.
- 2. Patient has a history of cathartic colon, laxative, or enema abuse.
- 3. Patient has a history of ischemic colitis.
- 4. Patient has a history of pelvic floor dysfunction.
- 5. Patient has a history of bariatric surgery for the treatment of obesity.
- 6. Patient has a history of surgery to remove a segment of the gastrointestinal (GI) tract at any time before the Screening Visit.
- 7. Patient has any history of myopathy, rhabdomyolysis, chronic myalgia, or familial history of hereditary muscular disorders.
- 8. Patient has been diagnosed with or has a family history of familial adenomatous polyposis, hereditary nonpolyposis colorectal cancer, or any other form of familial colorectal cancer.
- 9. Patient currently has any structural abnormality of the GI tract or a disease or condition that can affect GI motility, or any unexplained and clinically significant symptoms such as lower GI bleeding, rectal bleeding, heme-positive stool, iron-deficiency anemia, weight loss, or systemic signs of infection.
- 10. Patient has had any previous surgery involving the abdomen, pelvis, or retroperitoneal region during the last 12 months prior to Screening, with the exclusion of laparoscopic gallbladder surgery or appendix removal.
- 11. Patient has a history of diverticulitis or any chronic condition that could be associated with abdominal pain or discomfort and could confound the assessments in the study (e.g. inflammatory bowel disease, chronic pancreatitis, polycystic kidney disease, ovarian cysts, endometriosis, or lactose intolerance).
- 12. Patient has history of severe renal insufficiency defined as an actual or estimated glomerular filtration rate of < 30 mL/min/1.73 m² within the 6 months prior to Screening Visit.
- 13. Patient has any history of a medical condition or a concomitant medical condition that, in the opinion of the investigator, would compromise the patient's ability to complete the study safely or could confound the assessments in this study (e.g. uncontrolled hypothyroidism).
- 14. Patient is known to have elevated liver enzyme levels (aspartate aminotransferase [AST], alanine aminotransferase [ALT], alkaline phosphatase [ALP]) or creatine kinase levels that are ≥ 1.5 times the upper limit of normal (ULN) that have not been resolved within the 4 weeks prior to consent and/or these elevated levels are present at the Screening Visit laboratory assessment.
- 15. Patient has any abnormal laboratory results, electrocardiogram (ECG) findings, or physical examination findings deemed clinically significant by the investigator during the Screening Period.
- 16. Within 14 days prior to the Screening Visit, patient has used concomitant medications that are: (1) moderate-to-strong inhibitors of cytochrome P450 3A (CYP3A) and/or organ anion transporting polypeptide (OATP)1B1 (e.g. cyclosporine, verapamil, dronedarone, diltiazem, amiodarone, itraconazole, ketoconazole, posaconazole, voriconazole, clarithromycin, telithromycin, human immunodeficiency virus protease inhibitors, boceprevir, telaprevir, nefazodone, erythromycin, cobicistat-containing products); (2) other concomitant medications that are excluded from the lovastatin label (e.g. rifampin, colchicine, ranolazine); or (3) metformin or GLP-1 agonists. Patients should not take any of these concomitant

medications during the treatment phase of the study without contacting the investigator.

- 17. Patient has hypersensitivity to statins; or has used any statins, fibrates, > 1 g/day of niacin, or gemfibrozil within the 3 months prior to the Screening Visit.
- 18. Patient reports current chronic or frequent use of drugs known to cause constipation (e.g. narcotics) for the 3 months prior to Screening.
- 19. Patient has taken over-the-counter IBS treatments (e.g. laxatives) or proton pump inhibitors within 3 days prior to the Screening Visit.
- 20. Certain drugs used for the treatment of IBS (e.g. low dose tricyclic antidepressants) may be allowed at the discretion of the Medical Monitor provided the patient remains on a stable dose for one month prior to the Screening Visit and throughout the study with the exception of tegaserod, lubiprostone, linaclotide, metoclopramide, prucalopride, domperidone, plecanatide, CandiBactin, Atrantil, Allimax/Allimed within 2 weeks prior to the Screening Visit or antibiotics within 2 months prior to the Screening Visit.
- 21. Patient has used an opioid chronically or frequently within the 3 months prior to the Screening Visit and for the duration of the study.
- 22. Patient is currently enrolled in, or plans to enroll in, another clinical study or has used any investigational drug or device within 1 month before signing the ICF through the completion of the study.
- 23. Patient has previously participated in a SYN-010 study.
- 24. Patient has a history of alcohol or drug abuse within the 12 months prior to the Screening Visit.

7.3 Excluded therapies and medications, previous and concomitant

- Prior use of SYN-010.
- Concurrent use of another investigational drug or device therapy (i.e. outside of study treatment) during or within 4 weeks of trial entry (signing of the informed consent form).
- Major surgery within 30 days prior to start of study drug.

7.4 Removal of patients from therapy or assessment

The investigator may discontinue treating a patient with a study drug or withdraw the patient from the study at any time for safety or administrative reasons. The patient may decide to discontinue study drug or withdraw from the study at any time for any reason. The reason for discontinuation must be documented.

7.5 Withdrawal of patients from the study

Patients must be withdrawn from the trial (treatment and procedures) for the following reasons:

- Patient withdraws consent from study treatment and study procedures. A patient must be removed from the trial at his/her own request or at the request of his/her legally acceptable representative. At any time during the trial and without giving reasons, a patient may decline to participate further. The patient will not suffer any disadvantage as a result.
- Patient is lost to follow-up.
- Death.
- Pregnancy. Lovastatin is a pregnancy Category X drug and should not be taken during pregnancy. Female subjects who become pregnancy must immediately discontinue taking the study drug. Subjects will be instructed that known or suspected pregnancy occurring

during the study should be confirmed and reported to the investigator, who will then withdraw the female subjects from the study without delay. Protocol-required procedures for study discontinuation and follow-up must be performed on the subject unless contraindicated by pregnancy. The investigator should also be notified of any pregnancy occurring during the study and for 30 days after completion of the study. **Within 24 hours** of awareness of any pregnancy associated with study drug exposure during the study and for 30 days after the last dose of study drug, the investigator must record the event on the supplied pregnancy form and send it to the safety vendor. Any pregnancy will be followed to term or termination, and the status of mother and child will be reported on the pregnancy form after delivery. If delivery occurs after study closure, the outcome should be reported directly to the Sponsor.

Patients may be withdrawn from the study for the following reasons:

- The patient is non-compliant with study drug, trial procedures, or both, including the use of concomitant medications not prescribed by the study protocol.
- If, in the investigator's opinion, continuation of the trial would be harmful to the patient's well-being.
- The development of a secondary infection or other condition.
- Development of an intercurrent illness or situation which would, in the judgment of the investigator, significantly affect assessments of clinical status and trial endpoints.
- Use of illicit drugs or other substances that may, in the opinion of the investigator, have a reasonable chance of contributing to toxicity or otherwise skewing trial result.

Any patient removed from the trial will remain under medical supervision until discharge or transfer is medically acceptable.

In all cases, the reason for withdrawal must be recorded in the CRF and in the patient's medical records.

7.6 Screen failures

Patients withdrawn during the Screening Period due to abnormal ECG, liver function tests, creatine kinase level, opiate use, or pregnancy will not be allowed to repeat the Screening Period. All other patients withdrawn during the Screening Period will be reviewed and evaluated on an individual basis and may be allowed to re-enter the Screening Period at the discretion of the investigator and the study team.

8. Treatments

8.1 Randomization

Randomization will occur after a questionnaire collection period of at least 14 days, with compliance in fully responding to questions on at least 11 of the 14 days before the start of the Treatment Period.

After the successful completion of the Screening and Pre-treatment Period, eligible subjects will be randomly assigned in a 1:1:1 ratio to the following treatment groups: SYN-010 21 mg, SYN-010 42 mg, or placebo.

Patients will be assigned to the protocol specified treatments using a unique identification number which will be assigned when a patient is evaluated for inclusion into the study.

Randomization will be conducted through the research pharmacist using an online generator (www.sealedenvelope.com). Randomization will be in blocks of 6.

8.2 Investigational product

8.2.1 SYN-010

SYN-010 will be supplied by Synthetic Biologics, Inc. as a 21 mg or 42 mg capsule of lovastatin in a modified-release formulation.

SYN-010 is a capsule containing enteric-coated tablets of lovastatin designed to release drug in both the duodenal (pH 5.5) and ileocecal (pH 7.0) regions of the GI tract.

8.3 Comparator treatment to be administered

8.3.1 Placebo

The placebo is a capsule containing enteric-coated tablets without drug product that will be identical in appearance to SYN-010 and packaged in identical containers. The placebo will be supplied by Synthetic Biologics, Inc.

8.4 Full description and handling of treatments

8.4.1 SYN-010

SYN-010 will be supplied as a 21 mg or 42 mg capsule of lovastatin in a modified release formulation. SYN-010 is a green, size 1 HPMC capsule containing either 3 (21 mg) or 6 (42 mg) enteric-coated tablets of lovastatin (each 7 mg) designed to release drug in both the duodenal (pH 5.5) and ileocecal (pH 7.0) regions of the GI tract. The placebo is an HPMC capsule containing enteric coated tablets without drug product that will be identical in appearance to SYN-010 and packaged in identical containers.

8.4.1.1 General warning

SYN-010 capsules should not be chewed or opened.

The active ingredient of SYN-010 (lovastatin) is currently listed as a pregnancy category X drug and should not be taken during pregnancy. Female subjects who become pregnant must immediately discontinue taking study drug. Subjects will be instructed that known or suspected pregnancy occurring during the study should be confirmed and reported to the investigator, who will then withdraw the female subjects from the study without delay. The investigator should also be notified of any pregnancy occurring during the study but confirmed after completion of the study.

Clinical studies with the commercially-available cholesterol-lowering lovastatin formulation Mevacor[®] (Merck) showed that lovastatin, like other inhibitors of HMG-CoA reductase, occasionally causes myopathy manifested as muscle pain, tenderness or weakness with creatine kinase (CK) above ten times the upper limit of normal. Myopathy sometimes takes the form of rhabdomyolysis with or without acute renal failure secondary to myoglobinuria, and rare fatalities have occurred. The risk of myopathy is increased by high levels of HMG-CoA reductase inhibitory activity in plasma. SYN-010 is designed to limit systemic exposure of HMG-CoA reductase inhibiting lovastatin species and no myopathy or rhabdomyolysis were observed in Phase 1 or Phase 2a clinical trials with up to 12 weeks of SYN-010 42 mg dosing. Transient and reversible increases in serum CK were observed in two subjects treated with SYN-010 42 mg for 8 weeks in the Phase 2a clinical trial; however, these were deemed unrelated to study drug by the investigator and returned to normal without discontinuation of SYN-010.

Clinical studies with the commercially-available cholesterol-lowering lovastatin formulation Mevacor[®] (Merck) also found persistent increases (to more than 3 times the upper limit of normal) in serum transaminases occurred in 1.9% of adult patients who received lovastatin for at least one year in early clinical trials. When the drug was interrupted or discontinued in these patients, the transaminase levels usually fell slowly to pretreatment levels. The increases usually appeared 3 to 12 months after the start of therapy with lovastatin and were not associated with jaundice or other clinical signs or symptoms. SYN-010 is designed to limit systemic exposure to lovastatin species and SYN-010 21 mg and 42 mg doses did not cause clinically meaningful or persistent alterations to serum transaminase levels in Phase 1 or Phase 2a clinical trials.

8.4.1.2 Dose handling

All study drug has been manufactured according to Good Manufacturing Practice for Medicinal Products and the relevant regulatory requirements. The study drug will be distributed by PCI Pharma Services. All packaging and labeling operations have been performed according to Good Manufacturing Practice for Medicinal Products and the relevant regulatory requirements.

Study drug at the clinical study sites should be stored at controlled room temperature in a locked area accessible only to appropriate study personnel. Study drug bottles, and any unused study drug, will be retained by the study site until final reconciliation is completed, then destroyed by the study site according to local procedures. The investigator must provide an explanation for any missing bottles or missing capsules. Any missing bottles or capsules must be documented in the applicable source documentation and Accountability Log.

8.4.1.3 Dose calculation

SYN-010 doses were selected based on previous clinical experience in Phase 1 and Phase 2a clinical studies. These studies showed that SYN-010 provided continuous delivery of lovastatin lactone throughout the colon, and stool concentrations for the SYN-010 21 mg and 42 mg doses were equivalent to concentrations that inhibited methane production by ~60% and ~90% respectively in stool samples from an IBS-C patient *in vitro*. Moreover, these SYN-010 doses did not cause significant or persistent systemic effects on blood chemistry, hematology or urinalysis parameters over 12 weeks of dosing in Phase 2a clinical trials.

8.4.1.4 Dose administration

The study drugs, SYN-010 21 mg or 42 mg (active) or placebo (control), will be administered orally once daily at bedtime for 12 weeks.

8.4.1.5 Dose modification

No dose adjustments will be allowed.

8.5 Blinding

In compliance with applicable regulations, in the event of a SUSAR completed for patients on investigational drug SYN-010, the patient's treatment code will be unblinded and reported to the health authorities. SUSARs involving placebo would not be required to be submitted to the health authorities, however local and institutional regulations should be followed. Any safety reports completed, do not need to be unblinded before submitting to other investigators. Submission of safety reports to the ethics committee should follow local reporting regulations.

8.5.1 Emergency unblinding by the investigator

Unblinding may occur for emergency purposes only. The investigator should note that the occurrence of a serious adverse event or progressive disease should not routinely precipitate the immediate unblinding of the label. If unblinding is necessary for the treatment of a patient for a serious adverse event, every attempt should be made to contact the investigator prior to unblinding. If this is not feasible, then the investigator must be contacted within 24 hours of unblinding.

8.6 Drug logistics and accountability

All study drugs will be stored at the investigational site in accordance with Good Clinical Practice (GCP) and Good Manufacturing Practices (GMP) requirements and the instructions given by the clinical supplies department of the Institution and will be inaccessible to unauthorized personnel.

8.6.1 Storage

All investigational product will be kept in a locked area with access limited to study staff only. The locked area will be maintained under controlled temperature conditions at 20°C-25°C (68°F-77°F), and away from light and moisture.

8.6.2 Accountability

The investigator, or a responsible party designated by the investigator, must maintain a careful record of the inventory and disposition of the agent(s) (investigational or free of charge) using the Drug Accountability Record or another comparable drug accountability form.

8.6.3 Destruction and return

At the end of the study, unused supplies of SYN-010 and other investigational agents should be destroyed appropriately and according to institutional policies. Destruction will be documented in the Drug Accountability Record Form.

8.7 Treatment compliance

Upon receipt of the study drug, the investigator, or a responsible party designated by the investigator, will conduct an inventory of the supplies and verify that study drug supplies are received intact and in the correct amounts. A full drug accountability log will be maintained at the study site at all times. All discrepancies must be accounted for and documented.

Subjects will be expected to return all unused study drug and empty containers to the site at each clinic visit, and the number of capsules dispensed and returned will be documented by study staff.

The study personnel will account for all drugs dispensed and returned. All unused supplies of SYN-010 and other investigational agents will be destroyed appropriately and according to institutional policies. Destruction will be documented in the Drug Accountability Record form.

Subjects who are not compliant with treatment protocol, including laboratory evaluations, will be subject to withdrawal from the study at the discretion of the investigator.

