¹⁰Ongoing review and confirmation of patient PRO questionnaire compliance. Patients will complete the information contained in the REDCap system each day, assessing stool frequency, SBMs, CSBMs, and use of rescue medication or other laxative use; stool consistency using the Bristol Stool Chart; abdominal pain assessment using visual NRS scale (0-10) and visual Likert scale (0-4) for straining and bloating assessment. Questionnaires will also be completed weekly for the PAC-SYM questionnaire and Adequate Relief question.

¹¹EQ-5D-5L questionnaire will be completed in the REDCap system on Day 1 prior to study drug administration and at Week 12 or upon early termination.

¹²Pre-treatment stool sample can be collected any time during the week preceding and including Day 1 and will only be analyzed if the patient is randomized into the study; Day 84 stool sample can be collected any time during the week preceding and including Day 84. ¹³Patients are fasted overnight prior to lactulose breath testing. Lactulose breath test measures hydrogen, methane, hydrogen sulfide, and carbon dioxide levels.

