9.3.8 Daily diary and questionnaires

A study diary will be completed each day assessing stool frequency, SBMs, CSBMs, and the use of rescue medication (Appendix 13.3). Stool consistency will be assessed using the Bristol Stool Chart (Appendix 13.2). Severity of abdominal pain Will be assessed via visual NRS scale (0-10), while severity of bloating and straining will be assessed via Likert scale (0-4)

The PAC-SYM questionnaire and adequate relief question (Appendix 13.4) will be completed weekly. The EQ-5D-5L questionnaire (Appendix 13.5) will be completed on Day 1 prior to study drug administration and at Week 12 or upon early termination.

Subjects will be instructed on how to use REDCap to complete the assessments. During the Screening and Pre-treatment Period, subjects must complete the daily assessment for at least 14 days and have full responses to the questions on 11 or more of the 14 days before the start of the Treatment Period.

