9.3.13 Further safety

Individual subject stopping criteria: If any subject demonstrates (i) clinical signs of potential serious liver injury, hepatotoxicity, and/or hyperbilirubinemia jaundice, or (ii) myopathy/rhabdomyolysis with or without acute renal failure secondary to myoglobinuria, or (iii) a hypersensitivity reaction determined by the investigator to be associated with treatment, that subject should be withdrawn from therapy.

An increase in serum aminotransferases to > 3x ULN will be followed by repeat testing within 48 to 72 hours to confirm the abnormality and determine whether they are increasing or decreasing. If an abnormality develops during the course of the study that meets any of the following criteria, the subject should be withdrawn:

- ALT or AST > 8x ULN;
- ALT or AST > 5x ULN for more than 2 weeks;
- ALT or AST > 3x ULN and (total bilirubin > 2x ULN or INR > 1.5); or
- ALT or AST > 3x ULN with the appearance of fatigue, nausea, vomiting, right upper quadrant pain or tenderness, fever, rash, and/or eosinophilia (> 5%).

If an ECG abnormality develops during the course of the study that meets the following criteria, the subject should be withdrawn:

- Any QTc interval > 500 milliseconds, correction by Fridericia's formula;
- Any QTc interval increase from baseline > 60 milliseconds, correction by Fridericia's formula;
- New onset of arrhythmias such as ventricular tachycardia, multifocal ectopic tachycardia, ventricular triplets, supraventricular tachycardia, atrial fibrillation, second- or third-degree heart block, or bradyarrhythmias; or
- New onset of ECG signs of cardiac ischemia such as, but not limited to, ST segment abnormalities (elevation or depression).

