#### 3. ENDPOINTS

#### 3.1. PRIMARY EFFICACY ENDPOINT

The primary efficacy endpoint is the change from baseline in the weekly average number of complete spontaneous bowel movements [CSBMs] during the 12-week Treatment Period.

A CSBM is a spontaneous bowel movement [SBM] that is associated with a sense of complete evacuation. An SBM is a bowel movement that occurs in the absence of rescue medicine use or other laxative use (e.g. suppository or enema) on the calendar day of bowel movement or the calendar day before the bowel movement.

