#### 4.3. PER PROTOCOL ANALYSIS SET

The Per Protocol (PP) analysis set will consist of all subjects in the full analysis set who do not have any major protocol deviations. The major protocol deviations will include the following, but not limited to:

- Did not meet important eligibility criteria
- Missed more than 20% of planned medication

The Per Protocol (PP) analysis set will be identified before unblinding the study, and will be used in a secondary analysis of the primary endpoint and selected secondary endpoints.

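### Protocol 7.5 and 8.7 allow a non-compliant patient to be withdrawn from the whole study, and nothing keeps the daily diary going afterwards; the likely effect on the primary is small and the remedy is cheap

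*Protocol*

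**What the plan says.** Three protocol sections bear on removal.

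- Section 8.7: "Subjects who are not compliant with treatment protocol, including laboratory evaluations, will be subject to withdrawal from the study at the discretion of the investigator".
- Section 7.5 lists, among the reasons for which a patient may be withdrawn from the study: "The patient is non-compliant with study drug, trial procedures, or both, including the use of concomitant medications not prescribed by the study protocol".
- Section 7.4 separates two actions: "The investigator may discontinue treating a patient with a study drug or withdraw the patient from the study at any time". The grounds it gives are safety or administrative reasons.

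The diary supplies the primary endpoint. Section 9.3.8 says: "A study diary will be completed each day assessing stool frequency, SBMs, CSBMs, and the use of rescue medication". Table 1, footnote 10, says: "Patients will complete the information contained in the REDCap system each day". Neither makes the diary conditional on taking capsules, so a patient who stops drug but stays in the study is covered.

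For a patient who has left the study, the protocol provides medical supervision and a recorded reason (7.5) and one closing visit, at which the diary is returned (Table 1, Day 84 or early termination). The End-of-Study contact is for patients who complete treatment (5.3).

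The SAP analyses efficacy in the full analysis set by randomized treatment (4.2, 8). It already deals with non-compliance in two places. The per-protocol set excludes major deviations, among them: "Missed more than 20% of planned medication" (4.3). Laxative use is handled by definition: "An SBM is a bowel movement that occurs in the absence of rescue medicine use or other laxative use" (3.1).

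**The concern.** Withdrawal from the study serves no analytic purpose here, because the per-protocol set and the definition of a spontaneous bowel movement already absorb the two main kinds of non-compliance. Its effect is to end the diary. The full analysis set still includes the patient, so every later week becomes missing and is supplied by the rules in SAP 6.4.

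The trigger can also be related to outcome. A patient who takes a laxative outside the protocol because constipation persists, or who stops capsules for lack of benefit, fits the wording of 7.5. At stake are missing data that could have been avoided and may be informative. Multiple imputation and LOCF are planned as sensitivity analyses for the primary (SAP 8.1), but they model those weeks, whereas a continued diary would observe them.

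**Working it through.** **1. The plan's own figure.** Inputs from Protocol 6.8 and SAP 2.2: mean change 0.5 on placebo and 1.5 on active, SD 1.5, 50 per group, two-sided alpha 0.05.

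- Standard error of the difference = sqrt(2 x 1.5^2 / 50) = 0.30.
- Two-sample t-test power at a difference of 1.0 = 0.910. The stated 90% reproduces.

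**2. Primary endpoint.** Under SAP 6.4, a week with more than three missing days is missing and takes the average of the patient's observed weeks. I take this rule to govern weeks after withdrawal. SAP 6.4 also assumes no bowel movement and no rescue use where a daily question is unanswered, and I do not apply that assumption to whole weeks.

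Let w be the weeks observed and gap the difference between the patient's later and earlier weekly CSBM counts. The patient's 12-week value is then off by (12 - w)/12 x gap. The arm mean moves by that amount times the excess share of such patients in the arm.

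Assumptions, none of them from the documents as such:

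- gap = 0.5 CSBM per week;
- w = 4 or 8, the visits at which capsules are counted before Week 12;
- excess in one arm = 7.5%. This borrows 4/53 = 7.5%, the share withdrawn or terminated early so far (Protocol 6.6), which is pooled over arms and gives no reasons.

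| w | per patient | arm mean (x 0.075) | share of the SE of 0.30 | power if the difference narrows |
|---|---|---|---|---|
| 4 | 8/12 x 0.5 = 0.333 | 0.025 | 8% | 0.896 (difference 0.975) |
| 8 | 4/12 x 0.5 = 0.167 | 0.0125 | 4% | 0.903 (difference 0.9875) |

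At the extreme, a gap of 1.5 with w = 4 gives 8/12 x 1.5 x 0.075 = 0.075. That is 25% of the standard error, with power 0.863 at a difference of 0.925.

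**3. Responder endpoints.** Six of 12 weeks are needed (SAP 3.2). I enumerated all response patterns for w = 1 to 11.

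- Main analysis (missing weeks are non-response): at most w responding weeks, so w of 5 or less can never qualify.
- Sensitivity analysis with missing set to responder: at least 12 - w responding weeks, so w of 6 or less always qualifies.
- LOCF sensitivity analysis, w of 6 or less: if the last observed week is a response, the count is at least 13 - w, which is 7 or more. If not, it is at most w - 1, which is 5 or less. The last observed week alone decides.
- At w = 8 the observed weeks still matter: 6 of 8 are needed in the main analysis, and 2 of 8 with missing set to responder.

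One patient is 1/50 = 2.0 points of an arm's rate.

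**4. Reach.** The first 53 patients have all completed or left (49 + 4). A change can reach at most 150 - 53 = 97 patients, and none if enrollment does not resume. Only non-compliant patients whom the investigator would otherwise have withdrawn are affected.

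**The case against.** The strongest reply is that the protocol already offers the milder route. Both 7.5 and 8.7 are discretionary, 7.4 names stopping drug as an alternative, and a patient off drug but in the study keeps the diary. The laxative example is largely met as well: 8.8 has laxatives outside the protocol recorded, and the daily questionnaire (13.3) has a branch for them, so such patients are expected to stay and keep reporting. Counting weeks after dropout as non-response is a deliberate, prespecified rule with two sensitivity analyses. The responder endpoints are secondary and are formally tested only if both doses succeed on the primary (SAP 8.2.1).

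Most of this stands, and it limits the point to a modest one. It does not close the gap: nothing steers the investigator to the milder route, and no text provides for the diary once the other is taken.

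A reader might infer that power falls to about 86%. The documents do not support that. It needs a gap of 1.5, which equals the whole planned active-arm change and is three times the planned placebo change. It also needs the 7.5% one-arm excess, and a shift that narrows the difference. Patients who leave for lack of benefit have probably shown little change already. If their later weeks are similar, the gap is near zero and averaging the observed weeks loses almost nothing.

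A reader might also infer that the four early departures were withdrawals for non-compliance, or that one arm was favoured. No reasons are given, and the double blind limits steering by arm.

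**Conclusion.** The gap in the text is real. Withdrawal from the study for non-compliance is permitted, and the diary has no provision after it, although the full analysis set would use the data. The documents do not show that this has happened.

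The effect on the primary is likely small: a shift of 0.01 to 0.03 CSBM per week and power of about 90%, on the assumed gap, timing and one-arm excess. For the responder endpoints, each patient withdrawn within the first 5 weeks has a status fixed by rule, worth up to 2 points of a 50-patient arm. This is a cheap improvement, between optional and advisable, and not a threat to the primary conclusion. It matters only if recruitment resumes.

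**What to change.** For patients enrolled if recruitment resumes:

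- In 7.5 and 8.7, and for the administrative-reasons route in 7.4, make non-compliance a reason to stop study drug at most. Section 9.3.13 already uses this narrower form for three clinical stopping criteria: "that subject should be withdrawn from therapy".
- Ask the patient to continue the REDCap diary to Week 12 unless consent is withdrawn or contact is lost.
- State that the early-termination visit is done when drug is stopped, that no further dispensing or clinic tests are required, and that diary return moves to Week 12.
- Leave withdrawals for safety, pregnancy and withdrawn consent as they are. Compliance stays with the per-protocol set.

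The cost is amendment wording with sponsor agreement and EC/IRB approval (Protocol 12.1), possibly revised consent text, and reminders for a few patients off drug. The pause in enrollment is a convenient time. Little is recovered from patients who are non-compliant with the diary itself.

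The first 53 patients stay under the old rule. If blocks of 6 were filled in order, 53 = 8 x 6 + 5, which gives 18/18/17 by arm before the change and 32/32/33 after it, so the change falls almost evenly on the arms.
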